3. QRS
4. Known Coronary artery Disease
5. Previous Atrial Fibrillation
6. Hypertension
7. Diabetes
8. Peripheral Vascular Disease
9. Renal Failure
10. Systolic blood pressure
11. Diastolic blood pressure
12. Pulse pressure
13. New York Heart Association (NYHA) class
14. Left ventricular Ejection fraction (LVEF)

15. Pacing indications
16. Etiology of cardiomyopathy (if applicable)

Procedural Protocol

Patients will be prepped and draped in the usual sterile fashion. The 12 lead surface electrodes will be covered with sterile towels. Incision and subcutaneous pocket in the deltopectoral region will be created using standard technique.

Venous accesses are to be obtained by axillary vein or cephalic cut-down access utilizing modified Seldinger technique. Sheaths are to be placed into the venous system.

His Bundle Pacing is now included in the ACC/AHA guidelines for pacemaker implants. For those operators who chose to implant a pacemaker lead at the His bundle, the Medtronic 3830 lead is the standard of care. The region just distal to the His bundle is now being recognized as the Left bundle area pacing. Given both the His bundle and the right ventricle pacing, including the left bundle area, are standard of care with the 3830Medtronic Lead, there is no increased risk to the device use in this study. Additionally, the Medtronic 3830 lead has been FDA approved since July 12, 2018 for implantation of His bundle pacing and has an excellent safety and performance record.

For the ventricular lead placement, it is to be performed using the Select Secure (3830, 69 cm, Medtronic Inc.) pacing lead delivered through a fixed-curve (C315 HIS, Medtronic Inc.) or a deflectable catheter delivery system (Attain, Medtronic Inc.). The sheath is to be advanced, over the wire to the right ventricle. The 3830 leads will be inserted through the selected sheath and the tip of lead will be exposed from the sheath. The lead will be connected to the electrophysiological recording system on the atrial channel, with gain setting of 0.05 mV/mm, and a sweep speed of 50 mm/sec.

The lead and sheath will be withdrawn to the tricuspid valve annulus. A unipolar intracardiac electrogram will be recorded from the lead tip using electrophysiological recording system in order to identify a selective His bundle electrogram. Once a discrete His bundle electrogram is identified, unipolar pacing, at a pulse duration of 1.0 ms, will be initiated to elicit selective or non-selective HIS Bundle pacing based on criteria outlined by prior authors ([Vijayaraman, Chung, et al., 2018](#)). Effort will be made to achieve selective His bundle pacing, but if non-selective His bundle pacing can be elicited, this is acceptable.

Once selective or non-selective His bundle capture is demonstrated, the patient is randomized to His or left bundle area pacing for active fixation.

If the patient does not have the anatomy suitable for identifiable selective or non-selective HIS bundle capture, they will be removed from the study. Instead, they will undergo active fixation of the lead to the RV apex, septum, or left bundle area. This will be at the discretion of the operator.

If the patient is randomized, active fixation of the lead will be performed based on randomization to either His bundle or left bundle area pacing site.

If the left bundle area location is selected, the sheath and lead tip will be advanced to the anterior lower site of His bundle position, and then rotated in a counterclockwise fashion to place the lead tip in a perpendicular orientation to the IVS. To signify the site of left bundle area pacing, the following parameters should be sought; (1)A typical “W” with a notch at the nadir of the QRS complex in lead V1, or qR paced morphology in surface lead V1, (2) A shorter pacing-to-QRS interval than the initial His-bundle pacing-to-QRS interval, (3) and no His potential identified during intrinsic rhythm. Unipolar pacing will be performed at a pulse duration of 1.0 ms, and an output which allows for the narrowest complex QRS. The lead will then be screwed into the IVS by performing 4-5 initial clockwise revolutions of the fixation screw. To avoid penetration into the left ventricular cavity, intermittent observation of the impedance values, and anatomic septal penetrance by surface echo evaluation will be performed. An additional 4-5 clockwise revolutions will be performed, until impedance values start to drop, and the fixation screw has penetrated to the left septum on surface echo. Published expected impedance values and depth of penetrance have recently been published to be used as a template ([Vijayaraman P & Mascarenhas V, 2019](#)

) Afterwards, a small (<5 mL) contrast injection will be delivered through the sheath to verify septal penetration of the lead. Left bundle capture will be accepted if there is narrowing of the QRS when compared to pre-fixation QRS width at the proposed left bundle area site, or narrowing if the QRS complex at higher outputs indicating conduction system capture. A RBBB is expected, but not required for capture of the left bundle branch.

If the selective His site is to be used for active fixation, the lead will be placed with at least 5 revolutions of the screw into the myocardium.

The atrial lead will be inserted and actively fixed.

Device

The leads will be connected to Medtronic dual chamber pacemaker generator. The device will be placed in the pocket and the pocket will be closed with sutures in a standard manner as per the operator.

Echocardiographic Evaluation Protocol

A standard of care echo done within 3 months of the procedure will be used as the baseline echo. Data acquired from the echo will be and assessed by a single, non-blinded Cardiac Echocardiographer. Tissue doppler if not performed during the echo, post processing will be utilized if possible.

To evaluate the hemodynamic properties of the pacing site, echocardiography will be utilized.

Hemodynamic assessment will be obtained by collecting stroke volume at each site, utilizing the velocity time integral. The VTI will be obtained in the apical long axis view.

Left ventricular ejection fraction will also be assessed at each pacing site utilizing the biplane method of disks.

Tissue Doppler imaging will be used to assess longitudinal LV dyssynchrony. Myocardial velocity curves are to be obtained from the apical 2 and 3 chamber views. These views are selected to assess the anterior, inferior, lateral anterior-septal, inferior-septal, and inferior lateral left ventricular walls. The peak sustained myocardial systolic velocity (during the ejection phase) for each of the 4-LV segments is to be identified. The time to peak systolic velocity will be measured with reference to the onset of QRS complex.

The following data will be collected:

1. Left ventricular Ejection Fraction
2. Stroke volume (by VTI)
3. The peak sustained myocardial systolic velocity (during the ejection phase) for each of the 4-LV segments is to be identified:
 - a. Anterior
 - b. Anterior-Septal
 - c. Inferior-Septal
 - d. Inferior
 - e. Inferior-lateral
 - f. Lateral

Electrocardiographic evaluation

During the procedure, a 12-lead electrocardiogram will be available, and recorded while atrio-ventricular paced. The following will be collected:

1. The stimulation-to-QRS
2. QRS duration
3. QRS morphology
4. Pacing stimulus to left ventricular activation time (LVAT) in unipolar lateral precordial leads V4-V6

The following will be collected after active fixation, during the most narrow QRS morphology obtained:

1. The stimulation-to-QRS
2. QRS duration
3. QRS morphology
4. Pacing stimulus to left ventricular activation time (LVAT) in unipolar lateral precordial leads V4-V6

Procedural Data

Data collected will be:

1. Fluoroscopic time
2. Amount of contrast administered
3. Procedural time

Device Evaluation

Intra procedural data will be collected. After active fixation of the lead, the capture threshold will be collected. A pulse width of 1.0 ms will be used in all patients. Selective Left bundle branch (LBB) pacing (S-LBBP) is defined as only capturing the LBB without myocardial capture, with a discrete isoelectric component between the pacing stimulus and the onset of QRS complex in the electrocardiogram (ECG) and electrogram(EGM)s recorded by the EP system and the programmer. Nonselective LBB pacing (NS-LBBP) captured both the LBB and the local myocardium around the lead without the discrete isoelectric component. Selective HIS bundle (HB) pacing (S-HBP) is defined as only capturing the HB without myocardial capture, with a discrete isoelectric component between the pacing stimulus and the onset of QRS complex in the electrocardiogram (ECG) and electrogram (EGM)s recorded by the EP system and the programmer. Nonselective HB pacing (NS-HBP) captured both the HB and the local myocardium around the lead without the discrete isoelectric component. We will measure the pacing stimulus to left ventricular activation time (LVAT) in unipolar lateral precordial leads V4-V6 defined as the stimulus to the peak of the R wave and the paced QRS morphology.

Data Collected:

Unipolar

1. Selective Capture
2. Non-selective
3. Complete loss of capture
4. Impedance values at the site of active fixation will be collected
5. Sensed R wave amplitudes

Bipolar

1. Selective Capture
2. Non-selective
3. Complete loss of capture
4. Impedance values at the site of active fixation will be collected
5. Sensed R wave amplitudes

Post-Procedure Data

The following day, patient will receive a PA and lateral chest X-Ray.

A 12-lead electrocardiogram will be obtained while the patient is set to a parameter that ensures selective His ventricular pacing or the narrowest QRS achievable with left bundle area pacing, depending on the randomization group.

The following will be collected during pacing which yields the most narrow QRS:

1. The stimulation-to-QRS
2. QRS duration
3. QRS morphology
4. Pacing stimulus to left ventricular activation time (LVAT) in unipolar lateral precordial leads V4-V6

The device will be interrogated to obtain the following:

Unipolar

1. Selective Capture
2. Non-selective
3. Complete loss of capture
4. Impedance values at the site of active fixation will be collected
5. Sensed R wave amplitudes

Bipolar

1. Selective Capture
2. Non-selective
3. Complete loss of capture
4. Impedance values at the site of active fixation will be collected
5. Sensed R wave amplitudes

Follow-up

Patients will be assessed in the outpatient area at 3 (\pm 1 month), and 6 months (\pm 1 month), and 12-month (\pm 1 month) post implant. A 12-lead electrocardiogram will be obtained while the patient is set to a parameter that ensures selective His ventricular pacing or the narrowest QRS achievable with left bundle area pacing, depending on the randomization group.

1. The following will be collected at 3 months during pacing which yields the most narrow QRS, at 1.0 ms pulse duration: The stimulation-to-QRS
2. QRS duration
3. QRS morphology
4. Pacing stimulus to left ventricular activation time (LVAT) in unipolar lateral precordial leads V4-V6
5. Pacing burden

The device will be interrogated to obtain the following at 3month

Unipolar

1. Selective Capture
2. Non-selective
3. Complete loss of capture
4. Impedance values at the site of active fixation will be collected
5. Sensed R wave amplitudes

Bipolar

1. Selective Capture
2. Non-selective
3. Complete loss of capture
4. Impedance values at the site of active fixation will be collected
5. Sensed R wave amplitudes

The device will be interrogated to obtain the following at 6 months during pacing which yields the most narrow QRS, at 1.0 ms pulse duration::

1. stimulation-to-QRS
2. QRS duration
3. QRS morphology
4. Pacing stimulus to left ventricular activation time (LVAT) in unipolar lateral precordial leads V4-V6
5. Pacing burden

Unipolar

1. Selective Capture
2. Non-selective
3. Complete loss of capture
4. Impedance values at the site of active fixation will be collected
5. Sensed R wave amplitudes

Bipolar

1. Selective Capture
2. Non-selective
3. Complete loss of capture
4. Impedance values at the site of active fixation will be collected
5. Sensed R wave amplitudes

The following will be collected at 12 months, during pacing which yields the most narrow QRS, at 1.0 ms pulse duration:

1. The stimulation-to-QRS
2. QRS duration
3. QRS morphology
4. Pacing stimulus to left ventricular activation time (LVAT) in unipolar lateral precordial leads V4-V6
5. Pacing burden

The device will be interrogated to obtain the following at 12 months:

Unipolar

1. Selective Capture
2. Non-selective
3. Complete loss of capture
4. Impedance values at the site of active fixation will be collected
5. Sensed R wave amplitudes

Bipolar

1. Selective Capture
2. Non-selective
3. Complete loss of capture
4. Impedance values at the site of active fixation will be collected
5. Sensed R wave amplitudes

At 3 months the patient will have a limited echocardiogram while the patient is set to parameter that ensures AV synchronous, selective HIS pacing or the narrowest QRS achievable with left bundle area pacing, depending on the randomization group. The echo will be performed by sonographer and included in the budget. The following echo data will be collected at 3 months:

1. Left ventricular Ejection Fraction
2. Stroke volume (by VTI)
3. The peak sustained myocardial systolic velocity (during the ejection phase) for each of the 4-LV segments is to be identified:
 - a. Anterior
 - b. Anterior-Septal
 - c. Inferior-septal
 - d. Inferior
 - e. Inferior-Lateral
 - f. Lateral

4. The distance from the septal leaflet of the tricuspid valve to the entry point in the RV septum was measured from a standard 4-chamber view.
5. The length on penetration of the RV His or left bundle area lead into the myocardium
6. The degree of tricuspid regurgitation (TR)

Potential Risks

Adverse outcomes will be collected, and compared between the His bundle, and left bundle area pacing cohorts. These will include:

1. Lead pacing exit block
2. Threshold increase (defined as an increase in chronic pacing threshold >1 V at 1.0 ms)
3. Lead dislodgment
4. Need for lead revision.

Complications associated with device implantation will be recorded. Potential risks of any pacemaker implant, which may require additional reparative operations include

1. Excessive bleeding and pocket hematoma, requiring evacuation or transfusion)
2. Infection
3. Pneumothorax
4. Vascular injury
5. Cardiac perforation and tamponade
6. Lead dislodgement requiring revision
7. Radiation exposure
8. Pain at the incision site

Potential risks to the patient beyond those attributable to routine pacemaker implant are:

1. Additional contrast exposure
2. A theoretical interventricular septal puncture into the left ventricle with the active fixation of the screw if using the left bundle area location.

Interventricular septal puncture has been reported at a rate of 3 % in prior literature, which was corrected without any long term complication ([Vijayaraman P & Mascarenhas V, 2019](#)

)

Potential Benefits

Potential benefits are derived from recent studies ([Vijayaraman, Naperkowski, et al., 2018](#)), which include:

1. Decreased rate of hospitalization for heart failure
2. Increased LVEF

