For patients who require dual chamber pacing, patients will be randomized to His bundle versus left bundle area pacing for active fixation. We will evaluate the acute and follow-up capture threshold of His bundle versus left bundle pacing.

Objectives

Primary Objective

To compare 3 month follow up complete ventricular capture thresholds of His bundle pacing versus left bundle area pacing lead placement. Complete loss of capture will be measured with a width of 1.0 ms and during unipolar or bipolar output, whichever value is lower.

Secondary Objectives

To compare changes in left ventricular performance and mechanical synchrony, selective or non selective-His Pacing, left bundle area pacing, in patients who require ventricular pacing at 3 months.

The endpoints collected will be:

1. Ejection Fraction
2. Stroke volume
3. Mechanical dyssynchrony, characterized by the time to peak systolic velocity of the Left Ventricle (LV) myocardial walls, elicited by tissue Doppler:
 - a. Anterior
 - b. Posterior
 - c. Anterior-Septal
 - d. Anterior-Lateral
 - e. Lateral
 - f. Inferior-lateral
4. QRS duration

Other secondary endpoints collected will be:

1. 6 month complete loss of capture threshold as defined in the primary endpoint.
2. 12 month complete loss of capture threshold as defined in the primary endpoint

Methods

Design

Single center, open label, randomized pilot study to evaluate the complete ventricular capture thresholds of His Bundle versus left bundle area pacing.

Secondary analysis will focus on echocardiographic hemodynamic parameters of HIS pacing, versus left bundle branch pacing.

Based on previous studies ([Vijayaraman, Naperkowski, et al., 2018](#)) and our experience with non-selective and left bundle area pacing, a difference of 0.5 V at 1.0 ms in capture threshold at 3 month follow-up between His and left bundle area pacing sites, is to be expected. With a standard deviation of 0.5 V, This would require an enrollment of 20 patients to obtain a power of 0.8 to demonstrate

statistical significance. Thus we anticipate enrollment of 26 patients to evaluate differences in capture threshold between the studied pacing sites, and an expected 20% patient drop out.

Enrollment

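### The only echo reader the plan names is explicitly non-blinded, and nothing provides masked reading of the 3-month echo that carries the echo secondary endpoints

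*Combined protocol and SAP*

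**What the plan says.** The Design section describes a "Single center, open label, randomized pilot study to evaluate the complete ventricular capture thresholds" of the two pacing sites, and adds: "Secondary analysis will focus on echocardiographic hemodynamic parameters of HIS pacing, versus left bundle branch pacing". Ejection fraction, stroke volume and tissue Doppler dyssynchrony are listed as secondary endpoints at 3 months.

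The Echocardiographic Evaluation Protocol opens with the baseline study: "A standard of care echo done within 3 months of the procedure will be used as the baseline echo". The next sentence says that the echo data will be "assessed by a single, non-blinded Cardiac Echocardiographer". The section then sets out how stroke volume, ejection fraction and tissue Doppler timing are obtained, the first two at each pacing site.

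The Follow-up section covers the 3-month echo separately. On staffing it says only: "The echo will be performed by sonographer and included in the budget". Besides the functional measurements, that study collects "The distance from the septal leaflet of the tricuspid valve to the entry point in the RV septum" and "The length on penetration of the RV His or left bundle area lead into the myocardium", together with the degree of tricuspid regurgitation.

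**The concern.** Tracing the ventricle for biplane ejection fraction, outlining the VTI envelope and picking the peak on a tissue Doppler curve are all judgements. A reader who knows the arm can lean, without intending to, towards the site expected to perform better. Such a lean is systematic. It does not average out over patients, and the data cannot separate it from a treatment effect.

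An open-label design is understandable here, because the operator must know where the lead goes. That does not oblige the person who measures stored images to know the arm. The plan nevertheless specifies a non-blinded reader, gives no reason, and provides no masked second reading or repeatability check.

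The comparison of ventricular function and mechanical synchrony, apart from QRS duration, rests on these readings.

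**Working it through.** **Which echo does the reader sentence cover?** Two readings are possible.

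- *Baseline only.* The sentence comes directly after the one defining the baseline echo. The remark that follows it, on post-processing tissue Doppler that was not acquired, also fits a routine pre-implant study.
- *All study echoes.* The section is the general echo protocol. It asks for stroke volume and ejection fraction at each pacing site, which a pre-implant echo cannot supply. Under Randomization and Procedural Protocol, assignment is made during the implant, after His capture is shown. No arm exists when a pre-implant echo is recorded, so reader blinding matters chiefly for follow-up.

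The second reading is the more reasonable, but it is an inference. On the first, the 3-month echo has no named reader and no masking at all. Either way, nothing in the documents provides masked reading of the study that carries the endpoints.

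**Can the 3-month images reveal the arm?** Three features can:

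1. Lead entry point and penetration depth are measured on the same study.
2. Pacing during the echo is set according to the randomized arm.
3. Time to peak velocity is referenced to QRS onset, so the reader needs the ECG trace.

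No order is given for the functional and lead measurements.

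**Can the images reveal the visit?** Exclusion Criteria rule out previously implanted pacing devices other than a temporary transvenous pacemaker. The permanent lead is therefore present only after implant and marks the 3-month study.

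**Illustration of size.** The plan gives no figure to reproduce. Inputs:

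- From the documents: 20 patients required and 26 enrolled, 1:1, hence 10 or 13 per arm; significance level 0.05.
- Assumed: no true difference; a two-sided two-sample t-test; a reader shift of b SD in favour of one arm.

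In SD units the standard error of the difference is √(2/n). For n = 10 this is √0.2 = 0.447; for n = 13 it is √(2/13) = 0.392. The shift in standard errors is b/√(2/n), and the rejection rate comes from the noncentral t distribution with 2n − 2 degrees of freedom.

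| Assumed shift b (SD) | Shift in SE, n = 10 | False-positive rate, n = 10 | Shift in SE, n = 13 | False-positive rate, n = 13 |
|---|---|---|---|---|
| 0 | 0 | 5.0% | 0 | 5.0% |
| 0.10 | 0.22 | 5.5% | 0.25 | 5.7% |
| 0.25 | 0.56 | 8.3% | 0.64 | 9.4% |
| 0.50 | 1.12 | 18.5% | 1.27 | 23.2% |

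To give a sense of scale, if the SD of ejection fraction were 8 points (an assumption), a shift of 0.25 SD would be 0.25 × 8 = 2 points. At a fixed shift the rate is higher with 13 per arm than with 10, so a larger sample does not cure this bias.

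**The case against.** The strongest reply has four parts.

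- **The text does not say it.** A reader might infer that the documents have one unmasked person tracing the 3-month endpoints and measuring lead position. They do not say so. The non-blinded sentence is tied grammatically to the baseline echo, and the Follow-up section does not say who reads the images or who measures the lead. This stands as a limit on the claim. It does not remove the need for a change, because masking of the 3-month reading is absent on either interpretation.
- **Masking cannot be complete.** It is tempting to say that the reader could be blinded to both arm and visit at almost no cost. The documents do not support that. The permanent lead gives away the visit, its position and the paced QRS may give away the arm, and no cost basis is given. Hiding the trace except for an onset mark would need someone who sees the paced ECG to place the mark, which is a judgement too. All of this stands. Partial masking is still better than none.
- **The figures are assumed.** Neither the shift nor an ejection fraction SD is in the documents. The illustration uses an unpaired test, whereas Statistical Analysis describes only paired ones. Nor do the documents say which arm is expected to do better on echo, so a uniform shift across all echo endpoints is not established. This stands, and the table shows sensitivity only.
- **The stakes are limited.** This is a single-center pilot. Its primary objective is "To compare 3 month follow up complete ventricular capture thresholds of His bundle pacing versus left bundle area pacing lead placement", obtained by device testing. A reader might take unmasked echo reading as a threat to the main result; it is not one.

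**Conclusion.** The point holds for the echo secondary endpoints. The plan names one reader, describes that reader as non-blinded, and provides no masking for the 3-month study. Ejection fraction, VTI stroke volume and time to peak velocity are therefore open to reader bias. The capture threshold comparison is not affected.

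Applying the non-blinded sentence to the 3-month echo is a reasonable inference from its place in the general echo protocol, not an explicit statement. The size of any bias is unknown. Under the assumptions above, a shift of 0.1 to 0.5 SD at 10 per arm moves the false-positive rate from 5% to between about 5.5% and 18.5%. These figures are illustrative and do not estimate what will happen in this trial.

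This is a modest but worthwhile improvement: it replaces a stated bias-prone method with a better one, and needs no additional reader or echo.

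**What to change.** In the Echocardiographic Evaluation Protocol, replace the non-blinded description with *masked to treatment arm as far as feasible*, and state that this reader also reads the 3-month study. Then specify that:

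1. clips are coded, with patient and arm labels removed, and read in random order;
2. ejection fraction, VTI and tissue Doppler values are locked before the same reader makes the lead-position, lead-penetration and tricuspid measurements;
3. residual unmasking is stated as a limitation: the lead and the paced QRS may be visible, and masking to visit is not achievable.

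Cost: coding about 52 studies (26 patients × 2 echoes), fewer with drop-out. The main drawback is that masking will be partial, so the plan should not describe the readings as fully blinded.

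### The two apical views named for tissue Doppler do not cover the six walls listed: lateral and inferior-septal have no specified view, and lateral is a named endpoint wall

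*Combined protocol and SAP*

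**What the plan says.** Secondary Objectives defines endpoint 3 as "Mechanical dyssynchrony, characterized by the time to peak systolic velocity of the Left Ventricle (LV) myocardial walls, elicited by tissue Doppler", followed by six walls: anterior, posterior, anterior-septal, anterior-lateral, lateral and inferior-lateral.

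The Echocardiographic Evaluation Protocol sets the acquisition: "Myocardial velocity curves are to be obtained from the apical 2 and 3 chamber views". It continues: "These views are selected to assess the anterior, inferior, lateral anterior-septal, inferior-septal, and inferior lateral left ventricular walls". A comma is missing after the word lateral, but the data list below it separates lateral from anterior-septal, so the sentence names six walls. The same section then says: "The peak sustained myocardial systolic velocity (during the ejection phase) for each of the 4-LV segments is to be identified". It repeats that wording above a list of six walls.

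The Follow-up section uses the same four-segment wording and the same six walls for the 3-month limited echocardiogram. It names no tissue Doppler view of its own. A 4-chamber view does appear there, for another purpose: the distance from the tricuspid septal leaflet to the lead entry point "was measured from a standard 4-chamber view".

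For baseline: "A standard of care echo done within 3 months of the procedure will be used as the baseline echo". Its tissue Doppler is conditional: "Tissue doppler if not performed during the echo, post processing will be utilized if possible".

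**The concern.** The views, the segment count and the wall lists cannot all be right. If two apical views show four walls, a sonographer who follows the acquisition sentence to the letter has no instruction that yields lateral or inferior-septal velocities, yet both are listed for collection at baseline and at 3 months.

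This is more than a slip in a list. Changing four segments to six and tidying the wall names would still leave two listed walls with no view assigned.

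At stake is part of one secondary endpoint, in a pilot of 26 planned patients. The 3-month study is a limited echo done for the trial, so loops that are not specified may not be taken, or may be taken in some patients and not in others. Tissue Doppler that was never recorded may not be recoverable afterwards, and the protocol itself offers post-processing only where possible, in its text on the baseline echo.

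**Working it through.** No sample-size or power figure enters this point. The check is a count of walls by view, followed by a comparison of the lists.

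**Inputs from the protocol**
- Views named for tissue Doppler: 2 (apical 2-chamber and 3-chamber).
- Walls those views are said to assess: 6.
- Segments to be read: 4.
- Walls listed for collection at baseline and at 3 months: 6.

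**Input assumed (general echocardiographic knowledge, not in the documents)**
- Each apical view shows two opposing walls. 2-chamber: anterior and inferior. 3-chamber: anterior-septal and inferior-lateral. 4-chamber: inferior-septal and lateral.

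**Count**
- Walls shown by the named views: 2 views × 2 walls = 4.
- Listed walls with no view: 6 − 4 = 2 (lateral and inferior-septal), and 2/6 = 33%.
- With the 4-chamber view added: 3 views × 2 walls = 6, matching the list.

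The count of 4 equals the protocol's own segment count, which is some internal support for the assumed mapping.

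**Wall lists side by side**

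| Wall | Secondary Objectives | Echo protocol (sentence and list) | 3-month list in Follow-up | Named view that shows it |
|---|---|---|---|---|
| Anterior | yes | yes | yes | 2-chamber |
| Anterior-septal | yes | yes | yes | 3-chamber |
| Inferior-lateral | yes | yes | yes | 3-chamber |
| Lateral | yes | yes | yes | none |
| Inferior | no | yes | yes | 2-chamber |
| Inferior-septal | no | yes | yes | none |
| Posterior | yes | no | no | depends on naming |
| Anterior-lateral | yes | no | no | depends on naming |

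Four walls are common to every list: anterior, anterior-septal, inferior-lateral and lateral. Of these, lateral is the only one without a named view. Whichever list is kept, an endpoint wall is therefore left unprovided for. Inferior-septal is required by the echo lists but is not in the endpoint definition. Posterior and anterior-lateral are in the endpoint definition but not in the echo lists, and they cannot be placed until the names are settled.

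**The case against.** **The text does not exclude other views.** This stands. The protocol names two views and does not say that no other may be used, and its data lists ask for lateral and inferior-septal values, which gives a sonographer a reason to record a further loop. A reader might infer that these walls cannot be measured at either echo, or that the fields will be empty in every patient. The documents do not support that. They support only the statement that the plan specifies no view for these walls. Leaving it to individual initiative would make collection vary between patients, so the gap still needs closing.

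**Baseline is different.** This also stands. The baseline study is a standard-of-care echo whose views follow usual care. The two walls may be available there, depending on what was stored.

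**Perhaps four walls were intended.** The two views and the four-segment wording agree with each other, so cutting the lists to four walls would also remove the contradiction without changing acquisition. The documents do not settle the intention. But that route would drop the lateral wall, which appears in the endpoint definition and in every other list. Six is the reading that keeps the stated endpoint.

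**Lost wall-to-wall delays.** A reader might go further and count the pairwise delays that become unavailable, or single out septal-to-lateral delay as the main loss. The plan defines no wall-to-wall delay or dyssynchrony index. It specifies only the time to peak systolic velocity for each wall, referenced to QRS onset. Such counts would measure contrasts that nobody has planned, and nothing in the documents ranks septal-to-lateral delay above the others.

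**The anatomy is outside the documents.** True, and it is labelled as an assumption above. The conflict between four segments and six walls is visible without it.

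**Conclusion.** The point holds as a mismatch between the specified acquisition and the required data. Two of the six walls in the echo lists (33%), lateral and inferior-septal, have no specified tissue Doppler view. One of them, lateral, is part of the secondary endpoint as defined under Secondary Objectives. The consequence falls mainly on the 3-month echo.

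The conclusion rests on the standard mapping of apical views to walls, and on reading the acquisition sentence as the complete specification of views. It does not show that the measurements are impossible or that they will be missing.

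The reach is limited to mechanical dyssynchrony. The primary capture-threshold comparison, ejection fraction, stroke volume and QRS duration are untouched. The correction is worth making because it is small and protects data that might not be recoverable later.

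**What to change.** Make these changes in one edit:

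1. In the Echocardiographic Evaluation Protocol, name the apical 4-, 2- and 3-chamber views for the tissue Doppler curves.
2. State the same three views in the 3-month echo list under Follow-up, which currently names none for tissue Doppler.
3. Change the segment count from four to six wherever it appears in those two sections.
4. Make the wall lists under Secondary Objectives, in the Echocardiographic Evaluation Protocol and under Follow-up identical. This means deciding what posterior and anterior-lateral refer to, and whether inferior and inferior-septal belong in the endpoint.
5. For baseline, say that 4-chamber tissue Doppler is used where the standard-of-care echo stored it, and record where it did not.

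The cost is a few words of protocol text, plus one extra tissue Doppler loop and its reading per patient at 3 months: at most 26 × 1 = 26 loops if all planned patients attend. No new view is needed, because a 4-chamber view is already required at that visit for the lead distance. The ejection fraction method points the same way ("Left ventricular ejection fraction will also be assessed at each pacing site utilizing the biplane method of disks"), since biplane measurement conventionally uses the 4- and 2-chamber views, although the protocol does not say so.
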